7.2.7 Duration of Response

Duration of overall response: The duration of overall response is measured from the time measurement criteria are met for clinical CR or PR (whichever is first recorded) until completion of protocol treatment or early termination or the first date that recurrent or progressive disease is objectively documented (taking as reference for progressive disease the smallest measurements recorded since the treatment started).

[figure not shown]
The duration of overall clinical CR is measured from the time measurement criteria are first met for CR until the first date that recurrent disease is objectively documented.

Duration of stable disease: Stable disease is measured from the start of the treatment until completion of protocol treatment or early termination or the criteria for progression are met, taking as reference the smallest measurements recorded since the treatment started.

7.3 Pharmacokinetic and Pharmacodynamic Studies and Research Biopsy

Figure G provides an outline of the planned pharmacokinetic and pharmacodynamics studies and the time or research biopsy.

Figure G

7.3.1 Pharmacokinetic (PK) and Anti-Product Antibody (APA) studies

To investigate the pharmacokinetic interaction between TRC105 and everolimus, samples will be collected and concentrations of the agents measured on cycle 1 day 1 and cycle 2 day 1 at the following time points: predose, 1, 2, 4, 6, 24 hours, and cycle 1 day 4 pre-dose. Pharmacokinetic parameters to be estimated include maximum serum concentration (C_{max}), time of maximum serum concentration (T_{max}), area under the serum concentration versus time curve (AUC), terminal half-life ($T_{1/2}$), and clearance.

Serum for assessment of TRC105 anti-product antibody (APA) formation will be collected before dosing on cycle 1 day 1, every 4 weeks thereafter, 4 and 12 weeks following the last dose of TRC105 and concentrations will be determined by a validated ELISA⁵³.

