1.2.2. Secondary Endpoints

- a. Determine the rates of complete pathologic remission and downstaging achieved with the investigational treatment at the time of surgery.
- b. Determine the changes in tumor cell proliferation by means of changes in Ki67 expression and changes in serum concentration of markers of angiogenesis (VEGF-A, soluble VEGFR2, activin A and activin B, angiopoietin-1 and -2, TGF- β , soluble endoglin) before and after the investigational treatment and correlate with clinical, radiographic, and pathologic response.

c. Determine the C_{max} , T_{max} , AUC, $T_{1/2}$, clearance of everolimus and TRC105 when used in combination with letrozole.

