Pharmacokinetic properties: Everolimus is rapidly absorbed after oral administration, with a median time to peak blood levels (t_{max}) of 1.3-1.8 hours post dose¹¹. The extent of absorption is estimated at above 11%. The area under the blood concentration-time curve (AUC) is dose-proportional over the dose range tested while maximum blood concentration (C_{max}) appears to plateau at dose levels higher than 20 mg. The elimination half-life in cancer patients averaged 30 hours, which is similar to that in healthy subjects. Inter-patient variability is moderate with the coefficient of variation of approximately 50%. In healthy subjects, high fat meals reduced systemic exposure to everolimus 10 mg (as measured by AUC_{0-∞}) by 22% and the peak plasma concentration C_{max} by 54%. Light fat meals reduced AUC_{0-∞} by 32% and C_{max} by 42%. Food, however, had no apparent effect on the post absorption phase concentration-time profile. Steady-state trough levels are highly predictive of AUC, with a coefficient of determination of 0.96, as has been reported in renal transplantation patients. Everolimus is mainly metabolized by the cytochrome P450 isoenzyme 3A4 (CYP3A4) in the liver and to some extent in the intestinal wall¹¹. Everolimus is also a substrate of P-glycoprotein (P-gp). Therefore, absorption and subsequent elimination of systemically absorbed everolimus may be influenced by medicinal products that interact with CYP3A4 and/or P-gp. Strong CYP3A4 inhibitors (such as ketoconazole, itraconazole, ritonavir; **Appendix B**) and inducers (such as rifampicin, rifabutin; **Appendix B**) should be avoided.

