5.2.3 TRC105

Description of the drug. TRC105 is a chimeric anti-CD105 IgG1 antibody consisting of human C κ and C γ 1 constant regions with murine V κ and V H regions. TRC105 is composed of two light chains of 213 amino acids and two heavy chains of 448 amino acids and has an approximate molecular weight of 148 kDa.

Manufacturing. A high producing CHO cell line using media that is free of animal derived components has been developed for production of TRC105. The TRC105 currently in use in all clinical studies is CHO-produced. The manufacturing process uses conventional purification and filtration steps and concludes with the formulation of TRC105 in 20 mM L-Histidine/L-Histidine Monohydrochloride, 240 mM Trehalose, 0.01% Polysorbate 20 Formulation (25 mg TRC105/mL)⁸⁵.

Pharmacokinetic properties. In the phase 1 first-in-human dose escalation study of TRC105, the medication was detectable at all dose levels immediately after intravenous infusion³⁵. In patients enrolled at doses below 0.3 mg/kg every 2 weeks, circulating TRC105 was detectable but not measurable above the lower limit of quantitation of the assay (78 ng/mL). On an every 2-week

schedule, TRC105 was measurable above the target concentration that saturates CD105 receptors (200 ng/mL) for a duration of 4 hours at a TRC105 dose of 0.3 mg/kg, for 24 hours at 1 mg/kg, 120 hours at 3 mg/kg, and 188 hours at 10 mg/kg (Fig. 1). The observed terminal T_{1/2} was considerably prolonged following a single dose of 15 mg/kg compared with 3 and 10 mg/kg. Serum concentrations expected to saturate CD105 binding sites (≥200 ng/mL) were achieved continuously at 15 mg/kg dosed every 2 weeks and 10 mg/kg dosed weekly. At doses above 1 mg/kg, AUC increased supraproportionally with dose, whereas the C_{max} seemed to be dose proportional³⁵. TRC105 clearance was consistent with target mediated disposition, and decreased clearance at higher doses was related to target saturation⁸⁵.

Immunogenicity. Neither Human anti-murine antibody (HAMA) nor Human anti-chimeric antibody (HACA) were detected in patients treated with CHO-produced TRC105 which was administered at the 0.3, 1, 3, 10 and 15 mg/kg dose levels^{35,85} and will be used in the proposed study.

Pharmacodynamic properties. Please refer to the investigational brochure⁸⁵ for nonclinical pharmacodynamics studies with TRC105.

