Following the appropriate premedication regimen, the patient will receive TRC105 on day 1 and day 15 of every cycle. The first TRC105 dose will be split with 3 mg/kg administered on cycle 1 day 1 and infused over 4 hours (+/- 15 minutes) and 12 mg/kg (or 7 mg/kg if dose is de-escalated) administered on cycle 1 day 4 and infused over 2 hours (+/- 15 minutes), and then the full dose of 15 mg/kg (or 10 mg/kg if dose is de-escalated) given on cycle 1 day 15 and every 2 weeks thereafter and will be administered over a minimum of 90 minutes. The patient must complete at least one 4 hour infusion (+/- 15 minutes) without the development of any infusion reactions, in order to reduce the subsequent TRC105 infusion to 2 hours (+/- 15 minutes) and complete a 2 hour infusion (+/- 15 minutes) without the development of any infusion reactions in order to reduce subsequent TRC105 infusions to a **minimum of 90 minutes**. If the patient develops infusion reactions of any kind they should be managed appropriately (see [Section 5.3.2.1](#)) and the patient is not permitted to reduce the duration of the next planned infusion.

The rate of TRC105 infusion must not exceed 25 mg/min. When the i.v. bag containing TRC105 is empty, flush the i.v. line with a 20 mL normal saline. The dose level, time of transfer to i.v. bag, and the infusion start and stop times must be recorded in the source documents.

If the patient misses a TRC105 dose (i.e., ≥ 18 days between doses), the full premedication (including methylprednisolone) should be reinstated as per the initial infusion and TRC105 dose should be administered over two days as was done for the initial dose.

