3. Urinalysis should be obtained on screening and repeated as clinically indicated.
4. Research biopsy (core needle biopsy of the tumor).
5. Breast MRI is required by the protocol.
6. As clinically indicated after baseline diagnosis.
7. Within a week of surgery.
8. Continuation until the day prior to surgery.
9. Continuation no later than 4 weeks prior to surgery.
10. Samples will be collected and concentrations of the agents measured on cycles 1 and 2 at the following time points: pre-dose, 1, 2, 4, 6, and 24, hours, and cycle 1 day 4 pre-dose.
11. TRC105 anti-product antibodies (APA) will be collected before dosing on cycle 1 day 1, every 4 weeks thereafter, 4 and 12 weeks following the last dose of TRC105.
12. Markers of angiogenesis (VEGF-A, soluble VEGFR2, activin A and activin B, angiopoietin-1 and -2, TGF- β , soluble endoglin) will be measured on samples collected pre-dose, cycle 1 day 15, cycle 2 day 1, and prior to surgery.
13. Administered only if FSH, LH, and estradiol NOT within postmenopausal range at the time of enrollment.
14. In women with childbearing potential
15. Only in women receiving goserelin

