Snap Freezing: Do not Cut the tissue and simply ship as is. Place each core of tissue into a labeled individual 2.0 ml NALGENE® Cryoware™ cryovials. The label should contain the UAB clinical trial number (UAB 1514) followed by the subject's study number, as well as the date the specimen was collected. Do not place the patient's name or medical record number on the label. The container will become very cold. Do not handle with unprotected hands. Safety goggles should be use throughout the procedure. Snap freeze samples in liquid nitrogen. If not available, you may use an alcohol/dry ice bath. Fill pan about 1-2 inches deep with methanol. The depth should be enough to cover the height of the vial. Slowly add crushed dry ice until the boiling stops. The bath is now ready for use. Drop the sealed vials directly into the liquid nitrogen (LN₂) carefully. Leave the vials in the liquid nitrogen for at least one minute. Once frozen, transfer the samples using tongs or a large spoon to remove the vials from the liquid nitrogen and transfer to a -80 °C freezer until shipped.

C. Serum (PK, PD, APA)

1. Blood samples for the assays will be taken at the times described in the protocol. Serum will be obtained in red top serum separator tubes and will be sent to [name]'s Lab. **[name] lab should be notified of these samples. The laboratory address is:**

[name]'s Lab
Lab Contact: [name]
University of Alabama at Birmingham
CCC PK/PD Core Laboratory
[name]

2. **PK: A 5 mL blood sample will be collected pre-dose and 1, 2, 4, 6 and 24 hours post-dose on the days indicated within Table 7-1: Study Calendar. Samples will be separated and stored at approximately -70 °C.**

[name]'s Lab
Lab Contact: [name]
University of Alabama at Birmingham
CCC PK/PD Core Laboratory
[name]

APA: Anti-Product Antibody (APA) will be collected will be collected before dosing on cycle 1 day 1, every 4 weeks thereafter, 4 and 12 weeks following the last dose of TRC105

(Table 7-1: Study Calendar). Concentrations will be measured using validated ELISA methods. APA concentrations will be evaluated in the context of pharmacokinetic parameters and AE profiles. Samples will be separated and stored at approximately -70 °C.

[name]'s Lab

Lab Contact: [name]

University of Alabama at Birmingham

CCC PK/PD Core Laboratory

[name]

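### Full-dose TRC105 half-life and clearance, and everolimus terminal half-life, are not reliably estimable from the planned post-dose samples with descriptive analysis; separately, the interaction aim has no reference condition

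*Combined protocol and SAP*

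**What the plan says.** Section 1.2.2 (and the synopsis) lists Cmax, Tmax, AUC, half-life and "clearance of everolimus and TRC105 when used in combination with letrozole" among the secondary endpoints. Section 7.3.1 specifies that the half-life is the terminal one and opens with the aim of the sampling: "To investigate the pharmacokinetic interaction between TRC105 and everolimus".

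The schedule is the same wherever it is given. Section 7.3.1 samples on C1D1 and C2D1 "at the following time points: predose, 1, 2, 4, 6, 24 hours, and cycle 1 day 4 pre-dose". Note 10 to Table 7-1 has "pre-dose, 1, 2, 4, 6, and 24, hours, and cycle 1 day 4 pre-dose", and Appendix G has "A 5 mL blood sample will be collected pre-dose and 1, 2, 4, 6 and 24 hours post-dose". No TRC105 concentration is planned later than 24 h after the C2D1 dose.

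The first TRC105 dose is split (Section 6.1.3): "3 mg/kg administered on cycle 1 day 1 and infused over 4 hours (+/- 15 minutes"), with the remainder on day 4. The first undivided dose is on C1D15, then every two weeks. Section 5.2.3 reports that the TRC105 half-life "was considerably prolonged following a single dose of 15 mg/kg compared with 3 and 10 mg/kg", that AUC rises more than proportionally above 1 mg/kg, and that clearance falls at higher doses as the target saturates. Section 5.2.2 says of everolimus: "The elimination half-life in cancer patients averaged 30 hours". Under Section 4.3 letrozole, everolimus and TRC105 all begin at the start of treatment. Section 10.2 plans descriptive statistics and graphs for PK and names no population, interval or sparse-sampling model.

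**The concern.** A terminal half-life needs samples spread over the terminal phase. Clearance needs the AUC over a whole dosing interval at steady state, or to infinity after a single dose. At full-dose TRC105 the post-dose samples cover one day in fourteen. For everolimus they cover less than one half-life, and the day-4 sample includes later daily doses. If values are computed anyway, the listed endpoints will rest on extrapolation. They would then carry into the plots of PD against PK in Section 10.2 and the reading of anti-product antibodies against PK and adverse events in Appendix G.

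The interaction aim has a different problem. It needs a comparison in which one drug is present and then absent, and the design has none.

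**Working it through.** The plan gives no numerical justification for the PK schedule, so there is no figure to reproduce.

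**Inputs from the documents**
- Post-dose window 24 h; TRC105 interval 14 × 24 = 336 h.
- Everolimus half-life 30 h, daily dosing.
- TRC105 time above 200 ng/mL (Section 5.2.3): 24 h at 1 mg/kg, 120 h at 3 mg/kg, 188 h at 10 mg/kg, and continuous (at least 336 h) at 15 mg/kg every two weeks.

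**Assumptions**
- Independent log-scale measurement error of 15% (10-20% for everolimus); the documents give none.
- No numerical TRC105 half-life is given. An indicative range follows from a one-compartment rule, T½ = (t2 − t1)/log2(d2/d1):
  - 1 to 3 mg/kg: 96/1.585 = 61 h
  - 3 to 10 mg/kg: 68/1.737 = 39 h
  - 10 to 15 mg/kg: 148/0.585 = 253 h or more. This value mixes single-dose and repeated-dose data, so it is only a guide.

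**TRC105 at full dose, C2D1 post-dose samples alone.** 24/336 = 7.1% of the interval. With k = ln2/T½, the AUC0-24 share is (1 − e^(−24k))/(1 − e^(−336k)), and the fall from 6 to 24 h is 1 − e^(−18k). The last two rows come from simulated log-linear fits to the 4, 6 and 24 h samples with 15% error.

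| | T½ 39 h | 61 h | 253 h |
|---|---|---|---|
| Half-lives in 24 h | 0.61 | 0.40 | 0.09 |
| AUC0-24 as share of interval AUC | 35% | 25% | 11% |
| Fall from 6 to 24 h | 27% | 19% | 5% |
| Fitted T½ within 20% of truth | 30% | 19% | 5% |
| Slope zero or wrong sign | 3% | 12% | 39% |

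**TRC105, C1D4 sample.** It lies about 72 h after C1D1, which is 72/39 = 1.8 or 72/61 = 1.2 half-lives. That is usable, but it describes 3 mg/kg, and Section 5.2.3 says the kinetics differ at 15 mg/kg.

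**TRC105, C2D1 pre-dose trough.** It falls 336 h after the C1D15 dose. If it is taken as the 336-h value after C2D1 and joined to the C2D1 24-h sample, k = ln(C24/Ctrough)/312. I applied this without error to a linear one-compartment model with the protocol's 15 mg/kg sequence (3, 12, 15, 15 mg/kg on C1D1, C1D4, C1D15, C2D1). Half-life and clearance (dose/interval AUC) came back within about 1.5% for half-lives of 39-168 h. At 253 h, half-life was about 8% low and clearance about 8% high. With 15% error the CV of k is √2 × 0.15/(312k), or about 4%, 6% and 25% at 39, 61 and 253 h.

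**Everolimus**
- Window: 24/30 = 0.8 half-lives. Single-dose AUC beyond 24 h: e^(−ln2 × 24/30) = 57%.
- C1D4 pre-dose follows three daily doses. Its expected level is (1 − e^(−72k))/(1 − e^(−24k)) = 1.90 times the 24-h value, so it shows accumulation and not decline.
- Terminal slope from 4, 6 and 24 h: half-life within 20% of 30 h in 54%, 38% and 29% of profiles at 10%, 15% and 20% error. At 15%, the 5th to 95th percentiles are 18 to 95 h.
- At C2D1, 24 h is the whole daily interval, so AUC0-24 and apparent clearance (CL/F) are fully sampled.
- Accumulation: the expected C2D1/C1D1 ratio of AUC0-24 is 1/(1 − e^(−24k)) = 2.35. Solving back for an effective half-life in a group of 20, with 20% error per AUC, gives about 26 to 34 h if kinetics are linear and stable over time.

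**Interaction.** The two sampled days differ as follows.

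| | C1D1 | C2D1 |
|---|---|---|
| TRC105 | 3 mg/kg, first exposure | full dose after earlier doses |
| Everolimus | first dose | after four weeks of daily dosing |

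Both drugs are on board each time. Any change mixes TRC105 dose and everolimus accumulation with whatever interaction exists.

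**The case against.** A reader might infer that sampling simply stops at 24 hours and that these endpoints cannot be obtained at all. The documents do not support that. Section 7.3.1 includes the 72-h sample on C1D4 and a C2D1 pre-dose sample that is a 336-h trough after a full dose. Under linear kinetics that trough recovers TRC105 half-life and clearance well, as shown above. This part of the objection stands, and it makes much of the gap an unnamed method. It does not remove the point. The calculation treats a trough after the split dose and one full dose as steady state and assumes linear kinetics, whereas Section 5.2.3 describes target-mediated clearance. Section 10.2 names no such method. With no mid-interval sample, the slope is an average over the interval and not an observed terminal phase.

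A reader might also take everolimus clearance to be lost. It is not: the 57% applies to a single dose, and C2D1 covers the full daily interval. Only the terminal half-life is weak, and an effective half-life is available.

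A third tempting reading is that the interaction is a secondary endpoint defeated by the 24-h limit. It appears as the purpose of sampling in Section 7.3.1 and the synopsis, and not in Section 1.2.2. Its difficulty comes from the simultaneous start.

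Finally, PK is secondary and descriptive, and no escalation, MTD or phase 2 rule in Section 4 uses it. That stands and limits the severity.

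**Conclusion.** The point holds, at minor severity. With the planned post-dose samples and the stated descriptive analysis, full-dose TRC105 half-life and clearance and everolimus terminal half-life are not reliably estimable. An individual TRC105 half-life would fall within 20% of truth in about 5-30% of profiles, and an everolimus one in about 29-54%. The TRC105 figures rest on a half-life range derived from Section 5.2.3 and on an assumed 15% error; the everolimus figures rest on the stated 30 h and 10-20% error. The coverage figures, 7.1% of the TRC105 interval and 0.8 everolimus half-lives, need no assumption beyond the protocol's own numbers.

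Everolimus Cmax, Tmax, AUC0-24 and CL/F at C2D1 are unaffected. TRC105 values can be reported if they come from a named model and are labelled as such. The interaction aim fails for a separate reason, the lack of a reference condition.

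**What to change.** Amend Sections 7.3.1 and 10.2 and Table 7-1, and align the endpoint wording in Section 1.2.2 and the synopsis:

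1. **Everolimus.** Report Cmax, Tmax, AUC0-24 and CL/F at C2D1. Drop terminal half-life, or replace it with an effective half-life from accumulation between C1D1 and C2D1.
2. **TRC105.** Estimate clearance and half-life with a named population or interval model that uses the C2D1 pre-dose trough plus TRC105 assays at the existing C1D15, C2D15 and C3D1 visits. State that these samples are drawn before the infusion; the present text does not say so for the C1D15 PD serum. Take a PK tube where PD or antibody serum is insufficient, since Appendix G gives a volume only for PK. Report the values as model-based, because no mid-interval sample is taken at full dose.
3. **Interaction.** Describe the aim as PK in combination, compared descriptively with published single-agent data.

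The cost is a few extra assays and tubes at visits that already take place, a short modelling paragraph, and a slightly narrower PK claim. No visit is added and no treatment changes.

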7.3.2 Pharmacodynamic (PD) studies

Markers of angiogenesis (VEGF-A, soluble VEGFR2, activin A and activin B, angiopoietin-1 and -2, TGF- β , soluble endoglin) will be measured on serum samples collected predose, cycle 1 day 15, cycle 2 day 1, and prior to surgery.

7.3.3 Research biopsies

Formalin-fixed paraffin embedded tissue blocks from the patient's primary tumor collected for diagnostic purposes will be requested for all patients enrolled in the study at the time of registration. In addition, a research biopsy will be obtained at baseline, on cycle 2 day 1, and at the time of surgery if residual tumor. The goal is for 2-4 core biopsy specimens obtained using standard institutional guidelines for a diagnostic core biopsy of a breast mass. However, biopsy samples will preferably be obtained using a 14-18 gauge core needle. At least one core will be used to prepare a paraffin block (paraffin-embedded blocks or formalin fixed tissue) and at least one core will be immediately freeze (snap frozen individually for gene expression).

Snap frozen research biopsies will be sent to UAB Tissue Procurement where biopsies will be stored for batching. The batched biopsies will then be forwarded to HudsonAlpha Institute for Biotechnology. All samples will be indelibly labeled with the appropriate study number, and date of

acquisition; these data will be correlated with clinical efficacy including complete response and objective response. All samples sent to HudsonAlpha Institute for Biotechnology for comprehensive genomic analysis will be labeled with the appropriate study number only. Frozen research biopsy will be used for comprehensive genomic analysis such as Next-GEN genomic analysis. “Next-GEN genomic analysis will be done at HudsonAlpha Institute for Biotechnology in Huntsville, Alabama (Shared Facility of the UAB Comprehensive Cancer Center) by [name] group. No funding is necessary to conduct the evaluation in the laboratory at this time or macro-dissection; funds are needed only for shipping.

Researchers at HudsonAlpha Institute for Biotechnology led by [name] will obtain tissues from Drs. [name] and [name] at UAB from patients enrolled in the pilot Study. HudsonAlpha Institute for Biotechnology will analyze the tissues for several functional genomics features on a genome-wide scale, as well as whole exome DNA sequencing, to identify genetic variants. The functional genomics readout and genetic variation measurements will be assessed to help identify differences associated subtypes and/or responses to drug treatments. The researchers at Hudson will utilize their expertise in applying six different genome-wide functional genomics measurements, as well as whole exome sequencing, whole genome sequencing and specialized array-based genotyping to measure genomic and genetic variants for cancers, brain diseases, autoimmune diseases and drug responses. The functional genomics measurements will include the use of ultrahigh throughput sequencing to measure mRNAs and long non-coding RNAs (RNA-seq), microRNAs (miRNA-seq), DNA methylation (a combination of two approaches, RRBS and Methyl1450 arrays), protein:DNA interactions (ChIP-seq), chromatin markers (also ChIP-seq) and chromatin accessibility measurements (DNase-seq).

To measure DNA sequence variation, two types of ultrahigh throughput DNA sequencing will be performed: whole exome sequencing, where all the exons and exon:intron boundaries in the human genome are sequenced deeply; and whole genome sequencing, to be used on a modest number of samples due to expense. A combination of exome and whole genome sequencing with inexpensive genotyping of 1 million or more polymorphic DNA markers around the genome may be used to supplement the DNA sequencing and to improve the ability to identify large DNA sequence variants known as copy number variants.

Fifteen slides will be prepared from the paraffin blocks or formalin fixed tissue by [name] at UAB for analysis by conventional IHC of ER, PR, Her-2, EGFR, Ki67, apoptotic markers, and biomarkers of DNA repair such as H2AX and BRCA localization. All samples will be indelibly labeled with the appropriate study number, and date of acquisition; these data will be correlated with clinical efficacy including complete response and objective response. In addition, immunohistochemistry for pAKT and PTEN (markers of the PI3K/AKT/mTOR pathway), CD105 and CD31/CD34 (pan-endothelial markers), and NG2 and MCAM/CD146 (pericyte markers) will be conducted on the diagnostic research tissue, the research biopsy, and the final surgical specimen.

Any leftover study blood and tissue samples may be stored for future research studies. The subjects will consent to the future use of samples in the consent form for the study. Any samples will only be released for use in future studies after approval by the Principal Investigator and other regulatory bodies, as appropriate.

